Study Protocol

Otological Safety Profile of 100% Manuka Honey Application in Tympanoplasty: A Double-blinded Randomized Controlled Trial

Formulated on 5th May 2021

Revised on 20th November 2022

Background

Chronic suppurative otitis media (CSOM) is the chronic inflammation of the middle ear mucosa characterized by intermittent or continuous ototorhea from the ear canal that can be mucopurulent or serous in nature, through a perforation of the tympanic membrane that has occurred for two months or more. Two types of CSOM are recognized, a mucosal disease (safe type) and an epithelial disease (unsafe type).^{1,2}

CSOM is included in the ten most commonly found diseases in the field of Ear Nose Throat Head and Neck Surgery (ENT-HNS) in Indonesia, and ranks first in its prevalence. The prevalence of CSOM in Indonesia based on a survey by the Ministry of Health of the Republic of Indonesia in 1993-1996 was 3.1%,³ and according to the criteria of the World Health Organization (WHO) Indonesia was considered to have a high prevalence rate. When calculated based on the total population of Indonesia, which is currently 250 million, it is estimated that Indonesia has 7.8 million people who suffer from CSOM. Patient data from the Otology Division of the ENT-KL National Hospital [name] (RSCM) for the 2010-2020 period also showed a similar value, where CSOM was the number one cause of patient visits to the outpatient clinic and the most surgeries carried out each year.⁴ The impact caused by CSOM is very large, namely hearing loss, restrictions on activities related to water, as well as the risk of fatal complications.¹

Developments in the field of ENT-KL, especially otology, have made this disease treatable with a high success rate. One of the therapeutic options for CSOM is middle ear surgery. The aim of this surgery the prevention of reinfection through closure of the TM. However, graft failures can still occur. This failure can be caused by poor vascularization around the edge of the perforation due to chronic infection that results in low secretion of growth factors needed for the wound healing.

Throughout history, honey has been recognized for its healing properties. The use of honey for its medicinal properties dates back to 2200 BCE. The main content of honey is sugar (75-79%) and water (20%).^{11,14,15} Other ingredients are protein, vitamin B complex, minerals and antioxidants such as flavonoids, ascorbic acid, catalase, and selenium. Honey also contains enzymes such as invertase, amylase, and glucose oxidase.¹¹ Oryan et al.¹⁶ wrote that the therapeutic effect of honey on wound healing occurs through the following mechanisms: 1) antimicrobial activity; 2) debridement function; 3) anti-inflammatory function; 4) improving the immune system; 5) antioxidant function; 6) stimulate tissue regeneration and repair.

A number of studies have shown a positive effect of honey on cell proliferation, especially keratinocyte cells which play a very important role in the process of closing tympanic membrane

perforations. Chaudhary, et al.¹⁷ conducted a study using honey on human immortal keratinocytes (HaCaT) cultures. They found that the dilution of honey that gave the most effective effect was 0.1%. The wound healing rate in the cell layer was found to be the highest at 0.1% honey dilution and the lowest at 0.25% dilution. Calli et al.¹⁸ conducted a study on guinea pigs to evaluate the effect of honey on the healing of tympanic membrane perforations. They found that the group of animals that received honey drops showed a greater success of perforation closure than the control group that received drops of physiological saline solution. The results of histological examination also showed that the connective tissue was thicker and had a better woven arrangement in the group with the honey intervention.

Tympanoplasty is a surgical procedure that has a high level of difficulty and cost, and has a risk of failure. The failure rate for closure of the MT perforation ranges from 21% to 33%. One of the most common failures in this operation is that the MT perforation does not close due to poor vascularization and very low growth factor secretion in the perforated area. Honey has been widely studied for its benefits in wound healing,¹⁹ but the effect of Manuka honey on the tympanic membrane re-epithelialization process in CSOM patients has not been researched, given the differences in wound healing of the tympanic membrane and other parts of the skin. This research is expected to provide a new method that can increase the success of the tympanic membrane closure.

Research Objectives

- To test the otological safety of 100% medical grade manuka honey given at the time of tympanoplasty.

Research Design

This study uses a comparative, randomized and prospective clinical trial design to determine the effect of honey in increasing tympanic membrane re-epithelialization post tympanoplasty. The clinical study uses 100% medical grade manuka honey to determine the safety of its use in the healing process of tympanic membrane perforation after tympanoplasty. The subjects of the clinical study are CSOM patients of the mucosal type who underwent tympanoplasty at the Cipto Mangunkusumo hospital. During this research procedure, evaluation of the effect of ototoxicity will be carried out on all patients with the click stimulated ABR starting from the first subject. If an ototoxicity effect is indeed found, it will immediately be reported to an independent team outside the research team for an interim analysis to see the causal relationship with the treatment. Other side effects of administering manuka honey during and after the study reported by patients were immediately noted and evaluated.

Methods

The in vivo study was a randomized, controlled, double-blind clinical trial on adult patients (18 - <46 years old) diagnosed with tubotympanic chronic suppurative otitis media (CSOM) undergoing tympanoplasty at Cipto Mangunkusumo General Hospital (CMGH) from June 2021 – August 2022. Patients who had previously received surgical treatment for CSOM in the same ear or had recurrent or residual disease and those whose pathology showed suspicion of tumors were excluded from the study. Patients were randomly divided into intervention and control groups using the Robust Randomization App (RRApp)¹²² with a simple random sampling method and a ratio of 1: 1. Patients were blinded to the group assignments. During tympanoplasty, after filling the middle ear with gel foam and placing the graft, gel foam soaked in MH (MANUKApli topical gel, ManukaMed®) was placed in the external ear canal in the intervention group, while the control group only received a gel foam packing. The outer third of the ear canal was filled with an antibiotic tampon. The ear tampon is removed two weeks after the procedure and all patients applied six drops of 0.3% of ofloxacin twice daily for five days. Patient's symptoms were followed up at a weekly basis for the duration of six weeks. The BERA test was done at week 5. An audiometry test was done at week 6 to evaluate possible hearing loss. At 3 to 6 weeks post-tympanoplasty, patients were not given any ear drops.

For the in vivo study, the Mann-Whitney U test was used for unnormalized distributed continuous data. Categorical data were analyzed by using the Chi-square test with an alternative Fisher's exact test. The correlation of two numerical variables was analyzed by the Pearson correlation test for normally distributed data and Spearman correlation for data with non-normal distribution. The normality test was the coefficient of variation (COV) and the Shapiro-Wilk test. All tests were carried out in two-tailed with a significance level of 0.05. All data were processed and analyzed using Microsoft Excel 2021 and the Statistical Package for The Social Sciences (SPSS) version 26. All graphs were created using GraphPad Prism 9.1.0. This study was approved by the ethical committee of the Faculty of Medicine, Universitas Indonesia (no. KET 469/UN2.F1/ETIK/PPM.00.02/2021).

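### The aim is otological safety, yet no clinician-observed finding in the packed ear canal or on the graft is a defined safety outcome, and side-effect wording tied to honey does not assure equal collection in controls

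*Combined protocol and SAP*

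**What the plan says.** All references are to the combined protocol and SAP.

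- **Objective (Research Objectives).** A single aim is listed: "To test the otological safety of 100% medical grade manuka honey given at the time of tympanoplasty".
- **Site of exposure (Methods).** After the middle ear is packed and the graft placed, foam soaked in honey "was placed in the external ear canal in the intervention group". Controls receive foam without honey.
- **Unpacking (Methods).** "The ear tampon is removed two weeks after the procedure". No examination or finding is attached to that contact.
- **Hearing (Research Design and Methods).** "evaluation of the effect of ototoxicity will be carried out on all patients with the click stimulated ABR starting from the first subject". Methods puts the BERA test at week 5 and audiometry at week 6.
- **Symptoms (Methods).** "Patient's symptoms were followed up at a weekly basis for the duration of six weeks". The symptoms are neither listed nor graded.
- **Other side effects (Research Design).** "Other side effects of administering manuka honey during and after the study reported by patients were immediately noted and evaluated".
- **Independent review (Research Design).** Only a finding of ototoxicity leads to referral to a team outside the study.

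**The concern.** The tissues in contact with the honey are the canal skin and, on a natural reading of the packing sequence, the outer face of the graft. Some local harms there are signs that an examiner sees and a patient may not report: inflamed or macerated canal skin, granulation, fungal growth, a displaced graft. The plan defines none of these as an outcome.

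The side-effect rule does not close the gap, for two reasons. It admits only what patients report. It also speaks of effects of giving honey, so someone must judge cause before an event counts, and a control patient cannot by definition have such an effect. In a randomized safety comparison, events should be collected in the same way in both arms, with cause left to the comparison.

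At stake is the scope of the conclusion. The trial could report an otological safety profile when what it compared was hearing and patient-reported complaints.

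**Working it through.** No arithmetic decides this point, and the plan states no figure to reproduce. The check was to read the whole document for any clinician-assessed local outcome (otoscopy, canal skin, infection, discharge, granulation, graft position, perforation status) and set the result against each planned data source. Click ABR and BERA are taken to be the same test.

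| Planned source | Where stated | Timing | Captures an observed canal or graft sign? | Collected in both arms? |
|---|---|---|---|---|
| Click ABR / BERA | Research Design; Methods | Week 5 | No | Yes, all patients |
| Audiometry | Methods | Week 6 | No; a failed graft might affect hearing, but the test does not identify it | No arm restriction stated |
| Symptoms | Methods | Weekly, six weeks | No; pain or discharge may be reported, but nothing is examined | No arm restriction stated |
| Other side effects | Research Design | During and after the study | No; patient-reported only | Not assured; worded as effects of honey |

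Result: 0 of 4 sources defines a clinician-observed local finding. Tampon removal is described as a procedure, with no record of what is seen.

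**Does the background make local harm a negligible question?** It cites a keratinocyte culture study in which wound healing was fastest at 0.1% honey and slowest at 0.25%, and a guinea pig study that favoured honey. The trial uses 100% honey. The background also says that tympanic membrane healing differs from that of other skin, and gives a closure failure rate of 21% to 33%. None of this shows harm, and none of it gives a local event rate in patients. Local tolerance is therefore an open question that an otological safety trial would be expected to address.

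**Can a size be given?** No. There is no sample size, event count or margin, so no detectable or excludable rate of local harm can be derived.

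**Can the data still be collected prospectively?** Probably not. Methods places surgery between June 2021 and August 2022. Taking the latest date, 31 August 2022 plus 6 weeks (42 days) is 12 October 2022. The protocol revision is dated 20 November 2022, which is later.

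**The case against.** The other side has several fair points.

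1. *The control arm is not ignored.* Weekly symptoms are described in the common schedule without restriction to one arm, patients are blinded, and tests for categorical data are planned. This stands. A reader might infer that side effects have no counterpart in controls, or that a fair comparison is impossible. The text supports only that equal, cause-neutral collection is not assured.
2. *The graft is not wholly absent.* Research Design names re-epithelialization of the membrane as something the trial is to determine. This stands too, but no measure, assessor, time point or analysis follows. It is an undefined efficacy aim and does not serve as a harm outcome. The canal signs are the cleaner omission.
3. *Week 2 is not a view before shared treatment.* The plan says "The ear tampon is removed two weeks after the procedure and all patients applied six drops of 0.3% of ofloxacin", and a reader might infer that tampon removal is the last look before common antibiotic treatment. The documents do not support that: the tampon itself is antibiotic and is described without restriction to one arm, so shared exposure starts at surgery.
4. *The view at week 2 is uncertain.* The plan does not say who removes the tampon, whether the deeper foam comes out or has dissolved, or whether the graft can then be seen. A graft item can be asked for only where the graft is visible.
5. *Examination findings can be biased.* The trial is called double-blind, but only patients are said to be blinded. Yes/no signs read by someone who knows the allocation could favour one arm. This is a condition on the fix and does not remove the need for it.

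None of these supplies a defined, clinician-observed local safety outcome.

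**Conclusion.** The point holds in this form: no clinician-observed canal or graft finding is a defined safety outcome, and the wording of the side-effect rule does not assure equal, cause-neutral collection in the control arm. It should be corrected because the sole listed objective is otological safety and the exposure is local.

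Its size is structural: none of the four planned sources covers the treated tissue by examination. A reader might divide the two packed weeks by the six weeks of follow-up and treat the quotient as the share of events missed. It is only a share of the calendar and says nothing about events. A reader might also infer that local harms are the likeliest ones, but the documents give no frequency for any of them. Nor do they show that clinicians failed to look at the ears in routine care, only that what they saw is not a planned outcome.

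The conclusion assumes that the document is the whole plan and that symptoms means what patients say. If a separate case report form already records otoscopy in both arms, the remedy shrinks to naming those items as safety outcomes and rewording the side-effect rule.

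**What to change.** 1. **Replace the side-effect sentence in Research Design** with wording such as: *all otological adverse events in both arms, reported by the patient or observed by the clinician, regardless of suspected cause*. Compare them between arms with the Chi-square or Fisher's exact test already planned.
2. **Add a short yes/no otoscopy checklist in both arms** at tampon removal and at the week-6 visit: canal inflammation or maceration, discharge, visible fungal growth, granulation, and graft in place where visible. Existing staff unaware of allocation should complete it where possible.
3. **If follow-up is already complete**, as the dates suggest, extract the same items from existing clinic notes in both arms, without knowledge of allocation. If the notes do not hold them, limit the safety conclusion to hearing and patient-reported symptoms, and say so.

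Cost: one wording change and a few minutes of recording per patient at contacts already in the schedule, or a note review if done afterwards. The downsides are some recorded events unrelated to honey, and possible detection bias if the recorder knows the allocation.

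### Is the double-blind label unsupported because patients are the only party described as blinded?

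*Combined protocol and SAP*

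**What the plan says.** The title describes the study as "A Double-blinded Randomized Controlled Trial", and Methods repeats the claim: "The in vivo study was a randomized, controlled, double-blind clinical trial on adult patients". One sentence in Methods says who was masked: "Patients were blinded to the group assignments". No second party is named.

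Methods describes the arms as differing in what goes into the external ear canal. The intervention arm has gel foam soaked in the honey product, "while the control group only received a gel foam packing". No matching gel or vehicle is mentioned. The antibiotic tampon in the outer third of the canal comes out two weeks after surgery.

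Three kinds of safety assessment follow. For symptoms, patients' "symptoms were followed up at a weekly basis for the duration of six weeks". For hearing, "The BERA test was done at week 5" and "An audiometry test was done at week 6 to evaluate possible hearing loss". The person responsible is not identified for any of them. Research Objectives lists a single aim: "To test the otological safety of 100% medical grade manuka honey given at the time of tympanoplasty". Research Design adds that an ototoxic effect, if found, goes at once to an independent team outside the research team to judge causality, and that side effects reported by patients are noted and evaluated.

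**The concern.** Double-blind implies at least two masked parties, and the text names one. The operating team is unlikely to be the second, because the packing differs between arms and no sham gel is described. That leaves the outcome assessors or the analyst, and the document mentions neither.

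The gap touches the one listed objective. Symptom recording involves judgement, and so may the conduct or reading of a hearing test. The documents give no definition of hearing loss or ototoxicity to limit that judgement. The Background states a hope of benefit from honey, so a lean towards finding no harm is conceivable. The independent team would not catch a missed case, because it is called only after an effect has been identified. If the assessors knew the arm, a reassuring safety result could partly reflect that knowledge.

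**Working it through.** There is no planned figure to reproduce. The documents give no sample size, event rate or threshold for hearing loss, so no size of bias can be derived. The check is a reading of the text plus one count and two date comparisons.

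**1. Who is stated to be masked.** Label (title and Methods): double-blind. Named masked parties (Methods): patients. Named unmasked parties: none. The label therefore claims one more party than the text identifies. The text does not contradict the label; it leaves it partly unexplained.

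**2. How many assessments are in scope.** From Methods, taking one symptom follow-up per week:

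- symptoms: 6
- BERA: 1 (taken to be the click-stimulated ABR of Research Design)
- audiometry: 1
- total: 6 + 1 + 1 = 8 per patient

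None of the 8 has a named assessor or a described masking step. These are not 8 separate failures. They are one omission seen across three kinds of assessment, and in the 6 symptom contacts the source of the information is a blinded patient.

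**3. What bias would require.** An assessment is exposed only if (a) its assessor knew the allocation and (b) that assessor could influence the result. The number exposed is the count of assessments where both hold.

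| Case | Exposed, of 8 |
|---|---|
| All assessors masked | 0 |
| Only the symptom recorder knew the arm and could influence the record | 6 |
| As above, plus one of the two hearing tests | 7 |
| (a) and (b) hold for every assessment | 8 |

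The documents establish neither (a) nor (b) for any row. The range 0 to 8 states what is unknown; it does not estimate harm.

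**4. Whether the packing reaches the assessors.** The visible difference informs whoever places the foam. The tampon is removed at week 2, so BERA comes 5 − 2 = 3 weeks later and audiometry 6 − 2 = 4 weeks later. Nothing in the text says the ears look different by arm at those times, or that the surgical team runs or reads the tests. Tampon removal does fall inside the symptom follow-up, so it is a possible unblinding point for a symptom recorder who is present. The text does not say who is.

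**5. Whether a change could alter conduct.** Methods gives the period as June 2021 to August 2022, and the protocol was revised on 20 November 2022. Even if the last operation fell on 31 August 2022, six weeks (42 days) of follow-up would end on 12 October 2022, before the revision. New wording could describe the masking that took place but could not create it.

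**The case for a change.** The strongest case for acting is that adding the information costs almost nothing and the stakes are the trial's only objective. One or two sentences would tell a reader whether a safety conclusion came from masked assessment. The other safeguards do not replace them: randomisation does not protect outcome assessment, patient blinding does not control how a result is recorded or read, and the independent team sees only cases already found. It is also true that a double-blind label could be met by masking the analyst alone, leaving the assessors aware of the arm.

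All of that stands as a reason for the trial report to name the masked parties. It does not show a fault in the plan. If the assessors were masked, the remedy only writes down what already happened. If they were not, the proposed remedies rest on facts the documents do not supply:

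- Relabelling the trial as blinded for patients only would be false if the analyst, or some of the assessors, were masked.
- Re-reading BERA recordings without arm labels presupposes that the recordings were kept and that the first reading was unmasked; neither is stated.
- Limiting a safety conclusion has no text to act on, because the documents report no results.

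**Conclusion.** No change to the plan follows. The observation is accurate: the trial is called double-blind, patients are the only party named, and the masking of the symptom recorder, BERA reader, audiometry tester and analyst is not described. This is missing detail, not evidence that any assessor knew the allocation. Followed as labelled, with the second masked party being the assessors, the plan gives sound comparisons.

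The possible exposure is 0 to 8 of 8 scheduled safety assessments per patient, with no computable bias. The upper end needs every assessor both to have known the arm and to have been able to influence the result. The conclusion assumes that the double-blind label was used in good faith, that BERA and the click-stimulated ABR are the same test, and that the stated period covers all operations. It would not hold if other records showed that assessors had access to the allocation. In that event the affected assessments would need to be disclosed with the safety result.

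### No pre-operative hearing test is stated, and neither hearing loss nor ototoxicity is defined, so a patient's post-operative result cannot be classed as new inner-ear loss

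*Combined protocol and SAP*

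**What the plan says.** Otological safety of the honey is the only item under Research Objectives. Two sections of the protocol describe how hearing is checked.

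- **Research Design** says that all patients, counting from the first enrolled, are evaluated for ototoxicity with click ABR. It gives no time point and no criterion. If an ototoxicity effect is found, it goes at once to an independent team, which judges whether treatment was the cause.
- **Methods** gives the dates: "The BERA test was done at week 5" and "An audiometry test was done at week 6 to evaluate possible hearing loss". Both are after tympanoplasty.

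On who enters, Methods excludes "Patients who had previously received surgical treatment for CSOM in the same ear or had recurrent or residual disease" and those with suspected tumour. No exclusion concerns hearing. Background lists hearing loss first among the consequences of chronic suppurative otitis media.

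On analysis, Methods names the Mann-Whitney test for non-normal continuous data. It adds "Categorical data were analyzed by using the Chi-square test with an alternative" Fisher's exact test. It names no change score and no baseline adjustment.

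**The concern.** The escalation rule in Research Design works patient by patient: someone must decide that a given patient shows ototoxicity and pass the case on. That decision needs a reference value and a criterion, and the plan states neither.

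Without a reference, long-standing loss from the disease can be read as ototoxicity. A real drop from good hearing can also be overlooked because the final value still looks normal. Without a measure that separates inner-ear from conductive change, a conductive gain from the repair can hide an inner-ear loss, and a conductive loss from the surgery can be read as toxicity. A statement that no patient, or some number of patients, suffered hearing damage would then rest on a classification that the stated data do not support.

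**Working it through.** The plan gives no figure to reproduce, so this is a check of the text followed by simple arithmetic. I take BERA in Methods and click ABR in Research Design to be the same test. If they are not, the ABR has no date at all.

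**1. Inventory of hearing measurements**

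| Section | Test | Timing | Criterion |
|---|---|---|---|
| Research Design | Click ABR | not stated | none |
| Methods | BERA | week 5 after surgery | none |
| Methods | Audiometry | week 6 after surgery | none |

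Stated before surgery: 0. Dated after surgery: 2. Definitions of hearing loss or ototoxicity: 0. No section gives a threshold, a frequency range, air or bone conduction, a change rule, or a comparison with the other ear.

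**2. Does Research Design imply a baseline ABR?** No. The reference to the first subject concerns the order of patients, not a moment before surgery. The only dated recording is at week 5.

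**3. What a post-operative value contains.** For one patient, with a higher value meaning worse hearing:

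post = pre + inner-ear change + conductive change

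The stated data supply only the left-hand side.

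- *Pre* may be abnormal, because the disease causes hearing loss and no exclusion removes such patients.
- *Conductive change* may have either sign. The honey or control packing goes in "after filling the middle ear with gel foam and placing the graft", so the operation itself alters the sound-conducting structures. Background also gives closure failure of 21% to 33%, so the repair does not always succeed.

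The same decomposition applies to the week-5 ABR, the test that the plan ties to ototoxicity. It is one post-operative recording with no stated earlier one, and the plan does not say how a conductive contribution would be recognised.

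**4. Why a raw shift is not enough.** With a baseline, post − pre = inner-ear change + conductive change, which still mixes the two. The decibel values below are assumed, apply to audiometry, and only show the mechanism:

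- Masking: a 15 dB inner-ear loss with a conductive gain of 5, 10 or 15 dB gives a net shift of 15 − 5 = 10, 15 − 10 = 5 or 15 − 15 = 0 dB.
- Missed drop: with a 25 dB cut-off, a 15 dB drop from a baseline of 10 dB gives 10 + 15 = 25 dB, which is not above the cut-off.

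**5. What happens between arms.** Randomisation makes the expected pre-operative value equal in the two arms, so it cancels:

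E(post, honey) − E(post, control) = average effect of honey on the value measured

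The cost of leaving out the baseline is precision. In large samples, baseline adjustment multiplies the variance of the group difference by about 1 − ρ², where ρ is the correlation between pre- and post-operative values. For assumed ρ of 0.3, 0.5, 0.7 and 0.8 this is 0.91, 0.75, 0.51 and 0.36. The documents do not give ρ.

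**6. What can still be changed.** Surgery ran "from June 2021 – August 2022". Taking 31 August 2022 as the latest operation, six weeks (42 days) later is 12 October 2022. The title page reads "Revised on 20th November 2022", after that date. Only analysis and reporting remain open.

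**The case against.** The strongest reply has three parts.

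**The documents are silent; they do not show that a test was left out.** The protocol is short and describes no baseline assessment of any kind. A reader might infer that no pre-operative hearing test was done. The text does not support that: such tests may have been part of routine care. What stands is narrower. None is stated, and none is given a role in the definition or the analysis.

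**The trial compares arms, and that comparison is sound.** Pre-existing loss is expected equally in both arms and does not by itself create a false honey signal. This is right, and it limits the point to classing individual patients. A reader might infer that the randomised safety comparison is biased; the documents give no ground for that. The patient-level question remains because Research Design makes referral depend on it.

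**An independent team reviews suspected cases and may look beyond weeks 5 and 6.** Nothing in the protocol prevents this, and it helps with judging cause. It does not supply the criterion by which a case is detected and referred, so cases that were never flagged would not reach the team.

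One might also try to size the problem from the closure-failure range of 21% to 33%. That range describes closure, not hearing. Using it would require every patient to enter with loss and the loss to persist only where closure failed, and the documents support neither assumption.

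**Conclusion.** The point holds at patient level and should be fixed. The only dated hearing tests are post-operative. Neither hearing loss nor the ototoxicity effect is defined against a baseline or on a measure that separates inner-ear from conductive change. An abnormal week-5 ABR or week-6 audiogram therefore cannot be classed, from the stated data, as new inner-ear loss.

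The textual gap is certain. Its practical size is unknown, because the documents give no rate of existing loss, new loss or hearing gain after surgery. A reader might infer that most abnormal results would be old loss, but that would depend entirely on the rates chosen. The decibel and correlation values used above are assumptions that show direction only.

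The between-arm comparison of post-operative values remains valid on average, assuming that results are available alike in both arms. The loss of precision there is secondary.

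**What to change.** No new patient contact is needed. First, state whether pre-operative audiograms and ABR recordings exist for the operated ear.

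**If they exist:**
1. Define new hearing loss as a stated shift from the pre-operative value on a measure that separates inner-ear from conductive change, for example bone-conduction thresholds if recorded. Set the rule without reference to arm.
2. Compare the proportion with new loss between arms by the chi-square or Fisher test already named, and give the difference with its confidence interval. The control arm is what separates honey from surgery.
3. Report the number of patients without a baseline in each arm.
4. Optionally, adjust the week-6 values for the pre-operative value.
5. Label this as post hoc if results have been seen.

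**If they do not exist:** report the week-5 and week-6 results as between-arm differences with confidence intervals. Make no claim of new hearing loss or ototoxicity, or of its absence, in individual patients. If only audiograms exist, apply this branch to the ABR.

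**Cost:** low. Either charts are retrieved, probably with some missing baselines or bone-conduction values, or the conclusion becomes narrower.
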